#### 9.1.2. Categorical eGFR Endpoints

A 30% decline or eGFR < 15 is considered confirmed when the threshold is achieved at  $\geq 2$  visits. Patients who achieved the threshold at their last visit, but did not have a second confirmatory visit, are considered confirmed cases. Similarly, for a 30% or more increase in eGFR, a second confirmatory visit is needed with the exception of the last visit. Patients with a decrease from baseline in eGFR of  $\geq 30\%$  at the last on-treatment visit are considered to have a 30% or more decrease from baseline eGFR. In the event a patient has both an increase from baseline in eGFR of 30% or more and a decrease from baseline in eGFR of 30% or more, only the decrease from baseline is considered in composite endpoint analyses. Otherwise, if a patient

has more than one confirmed event, all events are counted in the categorical summaries. Confirmation of kidney failure components is based on all on-treatment eGFR values, irrespective of analysis windows.

The following categorical analyses of eGFR are summarized for the first year of treatment:

- The percentage of bardoxolone methyl versus placebo patients with an increase from baseline in eGFR of 30% or more after 48 weeks of treatment.
- The percentage of bardoxolone methyl versus placebo patients with a decrease from baseline in eGFR of 30% or more after 48 weeks of treatment.
- The distribution of changes from baseline in eGFR in bardoxolone methyl versus placebo patients after 48 weeks of treatment.

The following categorical analyses of eGFR are summarized for the second year of treatment:

- The percentage of bardoxolone methyl versus placebo patients with an increase from baseline in eGFR of 30% or more after 100 weeks of treatment.
- The percentage of bardoxolone methyl versus placebo patients with a decrease from baseline in eGFR of 30% or more after 100 weeks of treatment.

Newcombe's test for the common treatment difference and the corresponding confidence interval adjusting for the randomization strata for each criterion are reported.

### **9.1.3. Distribution of Changes in eGFR**

The proportion of patients at Week 48 and Week 100 with an eGFR change from baseline of 0 mL/min/1.73 m^2 to +10 mL/min/1.73 m^2 at 1-point increments of increased or decreased eGFR (e.g.,  $\geq 0$ ,  $\geq \pm 1$ ,  $\geq \pm 2$ ,  $\geq \pm 3$ ,  $\geq \pm 4$ ,  $\geq \pm 5$ ,  $\geq \pm 6$ ,  $\geq \pm 7$ ,  $\geq \pm 8$ ,  $\geq \pm 9$ ,  $\geq \pm 10$ ) is summarized by treatment group. The data are summarized similarly for 1-point increments of decreased eGFR to -10 mL/min/1.73 m^2.

A plot of the cumulative distribution of eGFR change from baseline at Week 48 and at Week 100 is generated. A Kruskal-Wallis rank sum test by treatment group of eGFR change from baseline at Week 48 and at Week 100 is used to examine the difference in distributions of eGFR changes between treatment groups at each of these visits.

Waterfall plots of eGFR change from baseline, labeled by treatment group at Week 48 and at Week 100 are generated. A cumulative distribution plot showing the distribution of change from baseline eGFR by treatment group will be generated at Weeks 48, 52, 100, and 104.

Each quartile of change from baseline in eGFR at Week 48, 52, 100, and 104 will be summarized descriptively.

## **9.2. Patient Global Impression of Change**

The Patient Global Impression of Change (PGIC) is a 7-point scale that asks patients to assess how much their illness has improved or worsened relative to a baseline state at the beginning of an intervention (Guy 1976). The PGIC is assessed by completing the following statement "Since I began trial treatment, my overall status is: very much improved (1), much improved (2), minimally improved (3), no change (4), minimally worse (5), much worse (6), very much worse

(7).” All PGIC values collected at each visit using the appropriate analysis windows (Section 6.5.4) are used; the number of patients in each category is summarized at each analysis visit by treatment group.

The analysis of PGIC assesses the distribution of responses in the bardoxolone methyl vs. placebo group at each analysis visit; the distributions are compared using ANCOVA with BASE\_eGFR, ACR\_STRAT, TRT\_EXP1 (or TRT\_EXP2 for Year 2), and treatment group as covariates and treatment as the fixed effect.

### **9.3. Clinical Global Impression - Improvement**

The Clinical Global Impression-Improvement (CGI-I) is a 7-point scale that asks the clinician to assess how much the patient's illness has improved or worsened relative to a baseline state at the beginning of an intervention (Guy 1976). The scale is assessed by completing the following statement “Compared to the patient’s condition at the start of the trial, this patient’s overall status is: very much improved (1), much improved (2), minimally improved (3), no change (4), minimally worse (5), much worse (6), very much worse (7).”

CGI-I is analyzed using the same methods specified for PGIC in Section 9.2.

### **9.4. Kidney Failure Composite Outcome**

#### **9.4.1. Primary Analysis of the Kidney Failure Composite Outcome**

The kidney failure composite outcome is defined as reaching one of the following:

- Confirmed 30% decline from baseline in eGFR; or
- Confirmed eGFR < 15 mL/min/1.73 m^2; or
- ESKD (initiation of maintenance dialysis or kidney transplant).

A 30% decline or eGFR < 15 is considered confirmed when the threshold is achieved at  $\geq 2$  visits. Patients who achieved the threshold at their last visit, and did not have a second confirmatory visit, are considered confirmed. The analysis uses initiation of maintenance dialysis or kidney transplant as reported in the database by the investigator. Patients with a decrease from baseline in eGFR of 30% or more at the last on-treatment visit are considered to have a 30% or more decrease from baseline eGFR. In the event a patient has both an increase from baseline in eGFR of 30% or more and a decrease from baseline in eGFR of 30% or more, only the decrease from baseline is considered in composite endpoint analyses. Confirmation of kidney failure components is based on all on-treatment eGFR values, irrespective of analysis windows. The date of the first eGFR meeting the kidney failure component is used in time-to-event analyses as the date of the event.

For the Year 1 analysis, the number and percentage of patients in each treatment group having a kidney failure composite by Week 52 are summarized using only on-treatment eGFR values. The proportion of patients with a given event is evaluated using Newcombe’s test accounting for ACR\_STRAT. Similarly, the number and percentage of patients in each treatment group having a kidney failure composite by Week 104 are summarized for the Year 2 analysis.

For the Year 2 endpoint (Section 3.1.2.3), a time-to-event analysis of the kidney failure composite is performed using only on-treatment eGFR values. Missing eGFR data are not

imputed for time-to-event analyses. Hazard ratios and 95% CIs are computed using Cox proportional hazards regression models. Patients who do not experience a confirmed event are censored for time-to-event analysis using the following conventions:

- patients who died from any cause prior to the end of the study are censored at the date of death;
- patients who discontinued the study prematurely, withdrew consent, or were lost to follow-up prior to the end of the study are censored at their last date of contact;
- patients who are alive and still being followed are censored on the study termination (for early termination) or study completion date at Week 104.

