#### 6.5.4.1. Off-Treatment Visit Windows

Patients who permanently discontinue study drug prior to Week 100 are asked to resume the planned assessments according to the study schedule in the protocol. Off-treatment values for clinical laboratory evaluations (Section 10.5), vital signs (Section 10.6), and electrocardiograms (Section 10.8) are those that occur after the last dose date for patients permanently discontinuing study drug prior to Week 100, and is summarized relative to their last dose of study drug. Off-treatment safety assessments are grouped for analyses according to the strategy in Table 4. Assessments that occur on the date of last dose are considered on treatment.

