##### **Year 2 Testing Sequence (all significance levels = 0.025)**

1. eGFR at Week 100 (primary at Year 2)
2. eGFR at Week 104 (key secondary at Year 2)

3. time-to first kidney failure composite (exploratory at Year 2)
4. distribution of PGIC at Week 100
5. distribution of CGI-I at Week 100

All remaining endpoints are considered “Exploratory” and presented with nominal significance levels for descriptive purposes only.

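### The kidney failure composite lets two non-consecutive low eGFR values form one confirmed event dated at the first dip; require consecutive on-treatment visits and date from that pair

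*SAP*

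**What the plan says.** SAP 9.4.1 sets the confirmation rule: "A 30% decline or eGFR < 15 is considered confirmed when the threshold is achieved at" two or more visits. It does not ask for consecutive visits and sets no interval. SAP 9.1.2 repeats the rule for the categorical eGFR endpoints.

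Two further sentences in 9.4.1 deal with the end of follow-up:
- "Patients who achieved the threshold at their last visit, and did not have a second confirmatory visit, are considered confirmed".
- For the 30% component, patients with such a decrease "at the last on-treatment visit are considered to have a 30% or more decrease from baseline eGFR".

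The pool of values is fixed by "Confirmation of kidney failure components is based on all on-treatment eGFR values, irrespective of analysis windows". The date is fixed by "The date of the first eGFR meeting the kidney failure component is used in time-to-event analyses as the date of the event".

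SAP 8.4 places the time-to-event composite third in the Year 2 fixed sequence, after Week 100 and Week 104 eGFR and ahead of PGIC and CGI-I. The level is 0.025, or 0.05 under SAP addendum 3.2 if both Year 1 endpoints are significant. The only planned sensitivity analysis (SAP 9.4.2) adds all-cause death and leaves the confirmation and dating rules untouched.

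**The concern.** Confirmation is meant to separate lasting loss of function from a passing low reading. A rule that accepts any two visits does this poorly. A patient who is low at Week 12, back above the threshold through Week 76 and low again at Week 88 is a confirmed case, dated Week 12. Nothing lasting began at Week 12.

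Dating at the first qualifying value is sound when the decline is sustained. It goes wrong when an early isolated dip is tied to a later, unrelated one. The single last value is a different matter: its date is reasonable, but it has no confirmation.

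At stake are the event count, the event times and the hazard ratio of an endpoint that would be reported as a kidney failure result and that gates two further tests. No planned analysis would show how far the result depends on these two rules.

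**Working it through.** **From the text alone.** SAP 8.8.1 lists 13 post-baseline on-treatment visits, from Week 1 to Week 100. Pairs that can confirm an event: 13 × 12 / 2 = 78. Adjacent pairs: 12. The widest pair is 100 − 1 = 99 weeks apart and would be dated Week 1.

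**Figures to reproduce.** The SAP states no event rate, hazard ratio or power for the composite. Its eGFR inputs (SAP 4.3) can be checked by normal approximation, with 78 and 79 patients and two-sided alpha 0.025 (z = 2.241):
- SE = 8 × √(1/78 + 1/79) = 1.277.
- Key secondary, difference 4.0: 4.0 / 1.277 − 2.241 = 0.891, so power is 0.81 (stated 80%). The 50%-power difference is 2.241 × 1.277 = 2.86 (stated 2.9).
- Year 2 primary, difference 3.3, averaging 13 visits with correlation 0.7: the variance factor is (1 + 12 × 0.7) / 13 = 0.723, so SE = 1.277 × √0.723 = 1.086. Then 3.3 / 1.086 − 2.241 = 0.80, and power is 0.79 (stated about 80%).

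The SD and correlation therefore behave as the SAP says.

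**Simulation inputs.**
- From the SAP: the 13 visits, SD 8 and correlation 0.7. These give a between-patient SD of 8 × √0.7 = 6.69 and a within-patient SD of 8 × √0.3 = 4.38.
- Assumed: baseline eGFR 50 or 60 (thresholds −15 and −18), mean decline 4 or 6 mL/min/1.73 m² per year, complete follow-up, and the 30% component only.
- Two covariance models: compound symmetry, as in SAP 4.3.1, and random slopes with the same within-patient SD, matched to SD 8 at Week 100. The slope SD is 6.69 / (100/52) = 3.48 per year.

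**Rules compared.** As written: low at two or more visits, or at the last visit, dated at the first low value. Alternative: low at two consecutive visits, dated at the first of the pair, or low at the last visit, dated there.

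| | Compound symmetry | Random slopes |
|---|---|---|
| As-written events resting only on non-consecutive dips | about 5–11% | 2–3% |
| Remaining events dated earlier as written | about 39–48% | 15–25% |

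Under compound symmetry the written rule gives events in about 13 to 38% of patients, and 18 to 26% of those events rest on a single last value. As outer bounds, non-consecutive events number from 157 × 0.13 × 0.05 = 1 to 157 × 0.38 × 0.11 = 6.6, or roughly 1 to 7 of 157 patients.

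**Effect on the hazard ratio.** Assume a 3.3 mL/min/1.73 m² benefit accruing linearly. Under compound symmetry, moving from the written to the alternative rule shifts the hazard ratio from about 0.55–0.62 to 0.49–0.57, and the test statistic rises slightly (for example, |z| from 1.37 to 1.53). Under random slopes both barely change. Dropping single last values as well lowers |z| (for example, from 1.37 to 1.11).

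**The case against.** The strongest reply is that the rule is the same in both arms, the endpoint is labelled exploratory, and it is tested only if Weeks 100 and 104 both succeed. Extra noise events pull the hazard ratio toward 1, and the larger event count can offset that. In a comparison with a rule that also required the next value to uphold a low last value, the hazard ratio moved by only 0.02 to 0.08, and the written rule had the slightly larger |z| in 15 of 16 scenarios. This stands against removing last-value events. It does not stand against the consecutive-visit rule alone, which costs essentially no power.

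The dating figure also depends on the noise model. Compound symmetry gives each patient the full between-patient spread from Week 1, which produces early dips. This stands, and is why both models are shown.

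A reader might infer several stronger points that the documents do not support:
- **Any passing dip becomes an event.** One isolated mid-study dip does not; it takes a second low visit or a low last value.
- **Formal testing means inflated type I error.** None is shown.
- **Later off-treatment values should overturn a last on-treatment event.** Such values exist: SAP 6.5.4.1 says "Patients who permanently discontinue study drug prior to Week 100 are asked to resume the planned assessments". But SAP 2.1 allows for reversible on-treatment effects, and SAP 12.1 expects off-treatment values to vary and correlate differently. Off-drug confirmation could therefore act differently by arm.
- **Adjacent assessments should be at least 4 weeks apart.** Weeks 1, 2, 4, 6 and 8 are 1 to 2 weeks apart, so sustained early loss would be missed.
- **The 25% screening limit shows measurement noise.** It is an eligibility cap, and baseline averages three values (SAP 6.4.1).

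**Conclusion.** The point holds in a limited form. The written rule can join unrelated dips into one confirmed event and date it at the first. No supplied text prevents this, and no planned analysis tests it. The misdating is the larger effect. Events resting only on non-consecutive dips are a small share, and the hazard ratio is modestly diluted under compound symmetry and hardly at all under random slopes.

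Larger shares arise if single last values are also removed or overturned. Much of that excess comes from the last-value exception, which is a trade-off between certainty and event count, not a clear error.

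The sizes rest on an assumed baseline, decline and noise model, with no discontinuation. The full protocol and the programming conventions were not available, so a spacing rule there cannot be ruled out. SAP 2.2 makes the SAP govern over the protocol where they are inconsistent.

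**What to change.** - In SAP 9.1.2 and 9.4.1, require the threshold at two consecutive on-treatment visits.
- In 9.4.1, date the event at the first value of that pair.
- Keep the last on-treatment value exception in the main analysis, dated at that last value. Flag these events, report their number by arm, and add a sensitivity analysis that excludes them.
- Report the present rule as a further sensitivity analysis in 9.4.2.
- Do not use Week 52, Week 104 or post-discontinuation values to confirm or refute on-treatment events, and do not impose a 4-week gap between adjacent assessments.

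The cost is SAP wording and re-derivation of the event flag and date from data already collected, settled before database lock. The downside is slightly fewer counted events.

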### **3.2. Clarification of Hierarchical Testing Strategy**

Section 8.4 of the SAP specifies that all endpoints tested at Year 1 and Year 2 will use a significance level of 0.025. Within each year, endpoints are tested following a fixed-sequence hierarchical testing strategy. The total significance level (0.05) was split between Year 1 and Year 2 as a strategy to reserve alpha to test Year 2 if the Year 1 testing sequence was not statistically significant. Formal testing in the sequence may proceed so long as statistically significant evidence of benefit continues to be shown. If in the sequence one endpoint does not show statistically significant evidence of benefit, formal statistical testing of subsequent endpoints will not occur.

As a clarification to the SAP, if there is a significant treatment effect for both Year 1 endpoints, then the significance level for Year 1 (0.025) remains available to be carried forward (recycled or passed along) to the Year 2 testing sequence. Thus, if both Year 1 endpoints are significant, the Year 2 testing sequence will be tested using a significance level of 0.05. This approach aligns with the fixed-sequence method in FDA guidance (Multiple Endpoints in Clinical Trials., January 2017).

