### 4.3. Sample Size Considerations

The Year 1 and Year 2 endpoints are not independent hypothesis sets. The endpoints are analyzed using a combination of the Bonferroni and fixed-sequence approaches for type 1 error control (Section 8.4).

The protocol specified enrollment of approximately 150 patients in the Phase 3 cohort. Actual enrollment in the Phase 3 cohort was 157. Sample size calculations for each year based on the actual number of patients enrolled are presented below.

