### **8.6.1. Primary Analysis of the Year 1 Primary Efficacy Endpoint**

The Year 1 primary endpoint of this study is the change in eGFR at Week 48 (i.e., the end of the first year of drug exposure). The change from baseline eGFR for patients treated with bardoxolone methyl is compared with placebo at Week 48 using mixed models repeated measures (MMRM) analysis, with baseline eGFR (BASE\_eGFR), ACR strata (ACR\_STRAT), and fraction of one-year exposure to treatment (TRT\_EXP1) as covariates and the following fixed factors: treatment group (TRT), time (i.e., VISIT; analysis visit number), the interaction between treatment and time (TRT x VISIT), and the interaction between baseline eGFR and time (BASE\_eGFR x VISIT) as covariates. Inclusion of the fraction of expected one-year exposure to treatment (Section 6.5.11) in the MMRM model as a covariate provides an adjustment for eGFR values collected from early discontinuation patients having less than 1-year of drug exposure.

The trial design separates discontinuation of study drug from discontinuation of study follow-up. Therefore, patients may discontinue early from study drug while continuing follow-up with study visits and assessments. The primary analysis of eGFR at Week 48 uses available eGFR values irrespective of whether or not a patient is receiving treatment. The MMRM analysis uses all eGFR values collected through Week 48 according to analysis visits 0, 1, 2, 4, 6, 8, 12, 24, 36, and 48 (Section 6.5.4). An unstructured covariance matrix is used.

In the event the MMRM model with an unstructured covariance structure does not converge, the following covariance structures are substituted, in the order listed. Each subsequent covariance structure is used only if each previous covariance structure is used and no previous model converged.

1. Heterogeneous Toeplitz covariance structure (assuming different variances at each time point and that measurements taken closer together in time are more highly correlated than those taken farther apart).
2. Toeplitz covariance structure (assuming measurements taken closer together in time are more highly correlated than those taken farther apart).
3. First order auto-regressive [AR(1)] covariance structure (assuming measurements taken closer together in time are more highly correlated than those taken farther apart, but the correlation is more constrained than the Toeplitz structure).

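### The kidney failure time-to-event analysis stops counting eGFR events when drug stops but keeps patients at risk, so the hazard ratio can favour the arm with more followed off-drug time

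*SAP*

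**What the plan says.** Section 9.4.1 of the SAP defines the composite as a confirmed 30% eGFR decline, a confirmed eGFR below 15 mL/min/1.73 m², or ESKD. For Year 2, "a time-to-event analysis of the kidney failure composite is performed using only on-treatment eGFR values", and confirmation also uses on-treatment values only. ESKD is taken as the investigator reports it, with no on-treatment limit. A Cox model gives the hazard ratio.

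Patients without an event are censored as follows:
- deaths, at the date of death;
- early leavers and withdrawals of consent, by the same rule as those "lost to follow-up prior to the end of the study are censored at their last date of contact";
- for everyone else, the rule in the SAP is that "patients who are alive and still being followed are censored on the study termination (for early termination) or study completion date at Week 104".

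No rule refers to the last dose. Stopping drug is also not leaving the study. Section 8.6.1 says that "patients may discontinue early from study drug while continuing follow-up with study visits and assessments", and section 6.5.4.1 says: "Patients who permanently discontinue study drug prior to Week 100 are asked to resume the planned assessments". Section 7.1 tabulates treatment discontinuation and trial termination separately. The only sensitivity analysis (9.4.2) adds all-cause death.

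Section 8.4 places this endpoint third in the Year 2 testing sequence, at 0.025. Under section 3.2 of the SAP addendum, if both Year 1 endpoints succeed, "the Year 2 testing sequence will be tested using a significance level of 0.05".

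**The concern.** After permanent discontinuation a patient remains in the Cox risk set, but two of the three event components can no longer occur. The hazard in that arm is diluted by time that is close to event-free by definition. If both arms have the same stop rate, timing and retention, and stopping is unrelated to prognosis, the dilution cancels. Equal proportions stopping are not enough, because early stoppers contribute more off-drug time than late ones, and stoppers who leave the study contribute less than those who stay.

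An arm could therefore look better on kidney failure because its patients stopped drug earlier or more often and were then well followed. The result would be a formal claim if the two preceding Year 2 tests succeed.

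**Working it through.** The plan gives no event count, power or hazard ratio for this endpoint, so there is no stated figure to reproduce.

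**Inputs from the documents.** "Actual enrollment in the Phase 3 cohort was 157" (78 and 79 by arm, section 4.3.1); dosing to Week 100; follow-up to Week 104; two-sided alpha 0.025 or 0.05.

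**Assumptions (no figures in the documents).** True hazard ratio 1; constant event rate of 8, 15 or 25% per year; stopping unrelated to eGFR; all stoppers followed and no ESKD, unless stated. Uniform stopping is spread over 100 weeks; early stopping is spread over the first 26 weeks.

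**Step 1: hand approximation.** If events count only on drug but risk time runs on, each arm's apparent rate is the true rate times the on-drug share of its risk time. The hazard ratio is then roughly the ratio of the two shares. A uniform stopper loses on average 50 of 100 weeks; an early stopper loses 100 − 13 = 87.
- 20% v 10% uniform: off-drug time 0.20 × 50 = 10 and 0.10 × 50 = 5 weeks per patient; 0.90 / 0.95 = 0.947.
- 30% v 10% uniform: 15 and 5 weeks; 0.85 / 0.95 = 0.895.
- 30% v 10% early: 26.1 and 8.7 weeks; 0.739 / 0.913 = 0.809.
- 30% early v 30% uniform: 26.1 and 15 weeks; 0.739 / 0.85 = 0.869.
- 25% uniform v 20% early: 12.5 and 17.4 weeks; 0.875 / 0.826 = 1.059. The arm with more stoppers is penalised because it has less off-drug time.
- 20% uniform in both arms, all v half of stoppers followed: 90/100 = 0.90 and 90/95 = 0.947; 0.90 / 0.947 = 0.95.

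**Step 2: Cox score equation.** For arm k, let P_k(t) be the proportion event-free and on drug, and F_k(t) the proportion stopped, followed and without a counted event. The counted event rate is d_k = λ(P_k + qF_k), where q is the ESKD share of the event rate. The risk set is Y_k = P_k + F_k. The fitted log hazard ratio β solves ∫[d₁ − (d₁ + d₀)·e^β·Y₁/(e^β·Y₁ + Y₀)]dt = 0. Ranges cover the three event rates and counting to Week 100 or Week 104.

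| Stopping (arm 1 v arm 0) | HR, q = 0 | HR, q = 0.2 |
|---|---|---|
| 20% v 10% uniform | 0.942–0.946 | 0.956–0.958 |
| 30% v 10% uniform | 0.886–0.893 | 0.912–0.916 |
| 20% v 10% early | 0.891–0.901 | 0.917–0.923 |
| 30% v 10% early | 0.786–0.802 | 0.837–0.846 |
| 30% early v 30% uniform | 0.842–0.864 | – |
| 25% uniform v 20% early | 1.062–1.082 | – |
| 20% v 20% uniform, all v half followed | 0.947–0.951 | – |
| 20% v 20% uniform, same retention | 1.000 | – |

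If half the stoppers leave the study in both arms, the bias roughly halves: 0.969–0.971 for 20% v 10% uniform and 0.873–0.884 for 30% v 10% early. Under this model, censoring at drug stop, or counting all events on and off drug, returns 1.000.

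**Step 3: a second method.** Patient-level simulation with exponential stopping times, two-year risks of 20% and 30%, and a fitted Cox model gave 0.94–0.95 for 20% v 10% and 0.88 for 30% v 10%.

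**Step 4: test size.** Simulation of 78 v 79 patients (40,000 trials per setting, q = 0, log-rank test, about 18–57 counted events) gave these two-sided error rates for this test taken alone:

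| Setting | At 0.025 | At 0.05 |
|---|---|---|
| 20% v 10% uniform | 0.024–0.028 | 0.051–0.055 |
| 30% v 10% uniform | 0.027–0.039 | 0.056–0.072 |
| 30% v 10% early | 0.038–0.082 | 0.074–0.133 |
| 30% early v 30% uniform | 0.031–0.050 | 0.060–0.089 |
| Censoring at drug stop, all of these | 0.023–0.026 | 0.048–0.052 |

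**The case against.** - **The error rates are for a test the SAP does not run on its own.** The composite is tested only after Weeks 100 and 104 both succeed. If the drug has no effect at all, that gate keeps false claims here rare. The rates in Step 4 matter when there is real benefit on mean eGFR but none on the composite, which is a narrow case. This stands, and the rates should be read that way. The bias in the reported hazard ratio remains.
- **The stopping scenarios are assumed.** This also stands. At 20% v 10% uniform the test size is essentially nominal; material inflation needs a large or early imbalance.
- **The target may be deliberate.** Sections 2.1 and 12.1 give reasons to treat off-drug eGFR as a different quantity. That supports leaving off-drug values out; it does not support leaving off-drug time in. One could read the analysis as comparing the chance of a counted event by Week 104, but the SAP does not state that target.
- **The model is simpler than the endpoint.** Section 9.4.1 requires two visits, with an exception at the last visit. Visit-based simulations with these rules gave about 0.77–0.93 under the SAP rule and 0.96–1.00 with censoring at drug stop. So the visit rules do not remove the bias, the tabulated ranges are not bounds, and the repair is exact only in the simple model.
- **Unseen documents.** The programming conventions and the full protocol were not available. They could affect implementation, but section 9.4.1 states its own censoring list.

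**Conclusion.** The concern holds. As written, the analysis pairs on-treatment event counting with risk time that continues after drug is stopped, and no other rule or sensitivity analysis corrects this. The hazard ratio can be biased toward the arm with more followed off-drug time. The direction and size in this trial cannot be known from the documents. Under the assumptions above, with stopping unrelated to prognosis, the shift is about 5% for a modest imbalance and about 20% for a large early one. It is smaller if ESKD makes up part of the events or if stoppers leave the study. The effect on test size is small for modest imbalance. The Week 48, 52, 100 and 104 analyses are untouched. It should be fixed because the endpoint carries formal alpha.

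**What to change.** Make counted events and risk time cover the same period, and state the estimand. There are two options:

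1. **Keep the on-treatment target (the smaller change).** Censor event-free patients at the end of on-treatment assessment, and say whether ESKD after that point counts. State that only permanent discontinuation triggers this censoring, not the planned Week 48 to 52 break or a temporary interruption (addendum section 4.4.3). Give one cut-off: the SAP uses the last dose in sections 6.5.4.1 and 8.6.2.2, but less than 14 days after it in the Table 4 footnote and section 9.1.1.2. Say how the last-visit rule works with this censoring.
2. **Count confirmed eGFR events on or off drug, with the existing censoring.** State how values from the planned withdrawals at Weeks 52 and 104 are handled, including under the last-visit rule.

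Choose one as primary before Year 2 unblinding and report the other as a sensitivity analysis. Each has a weakness. Censoring at drug stop is informative if patients stop because eGFR is falling. Off-drug values can act differently in the two arms if the drug effect is partly reversible.

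The cost is SAP wording and programming. No new data collection is planned for, since patients who stop drug are already asked to continue the scheduled assessments.
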